ZIIP Acne Protocol October 5, 2020

Evaluation of the Safety and Efficacy of an Acne Treatment Device

| STUDY NUMBER | DCS-46-20 |
|----------------------------|--|
| INVESTIGATOR | [name] |
| STUDY SITE | Dermatology Consulting Services, PLLC [name] T [contact] F [contact] [contact] |
| INSTITUTIONAL REVIEW BOARD | Allendale Institutional Review Board (AIRB) [name] T [contact] F [contact] |
| SPONSOR | ZIIP Inc. |
| INVESTIGATIONAL DEVICE | ZIIP Device |
| SPONSOR PRIMARY CONTACT | [name] |
| STUDY DESIGN | Monadic device, historical control |
| VERSION NUMBER | 6 |

This document is confidential and contains proprietary information of Dermatology Consulting Services, PLLC. Neither this document nor any information contained herein can be reproduced or disclosed to others without written consent of Dermatology Consulting Services, PLLC.

| Dermatology Consulting Services, PLLC | PAGE 2 of 2 |
|--|-------------|
| PROTOCOL NUMBER: DCS-46-20 | |
| STUDY TITLE: Evaluation of the Safety and Efficacy of an Acne Treatmen | nt Device |
| PROTOCOL SYNOPSIS AND BUDGET DATE: August 1, 2020 | |
| PROTOCOL DATE: October 5, 2020 | |
| ANTICIPATED STUDY RUN DATES: TBD | |
| ANTICIPATED FINAL REPORT DATE: TBD | |
| This document represents the final approved protocol ready for IRB su | bmission. |
| Representative Date ZIIP | |

Date

[name].
Primary Investigator
Dermatology Consulting Services, PLLC

[name]

STUDY NUMBER 1

- 1. Error! Bookmark not defined.
- 2. Error! Bookmark not defined.
- 3. Error! Bookmark not defined.
- 4. Error! Bookmark not defined.
- 5. Error! Bookmark not defined.
- 6. Error! Bookmark not defined.
 - 6.1 Error! Bookmark not defined.
 - 6.2 13
 - 6.3 Error! Bookmark not defined.
 - 6.4 Error! Bookmark not defined.
 - 6.5 Error! Bookmark not defined.
- 7. Error! Bookmark not defined.
 - 7.1 15
 - 7.1.1 Error! Bookmark not defined.
 - 7.1.2 Error! Bookmark not defined.
 - 7.1.3 Error! Bookmark not defined.
 - 7.1.4 15
 - 7.1.5
 - 7.1.6 15
 - 7.2 15
 - 7.2.1 16
 - 7.2.2 16
 - 7.2.3 17
 - 7.2.4 17
 - 7.2.5 18
- 8. Error! Bookmark not defined.
 - 8.1 Error! Bookmark not defined.
- 9. Error! Bookmark not defined.
 - 9.1 Error! Bookmark not defined.
- 10. Error! Bookmark not defined.
 - 10.1 Error! Bookmark not defined.
 - 10.2 Error! Bookmark not defined.
 - 10.3 Error! Bookmark not defined.
 - 10.4 Error! Bookmark not defined.
 - 10.5 Error! Bookmark not defined.

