1. PROTOCOL SYNOPSIS

| Title of Study: | Evaluation of the Safety and Efficacy of an Acne Treatment Device |
|--|---|
| Study Period: | 12 weeks |
| Test Device and Application Instructions: | ZIIP Device (active) -400 microamps direct current, applied 3 days per week on non-consecutive days, on all areas afflicted by acne The following instructions will be provided: 1. Both silver probes must come in contact with skin throughout treatment. 2. Slowly make continuous circles with the top probe (the one farthest away from the charging port) over acne within each facial zone. **NOTE: Instructional video will be provided for participants to follow** 3. Treat each facial zone for 1 minute. Your device will beep and vibrate at the one minute mark to indicate that treatment of that zone is complete. Only treat the acne zone(s) identified for treatment. 4. After treatment, wipe your device clean with a tissue, being careful to avoid the charging port. Spray the device and a second tissue lightly with rubbing alcohol and wipe again, remaining careful to avoid the charging port. 5. Store safely away from water, moisture or debris. |
| Ancillary Product and Application Instructions: Objective: | Electroconductive Media Apply as a thin layer to all facial areas afflicted with acne The objective of this study is to demonstrate the safety and efficacy of a novel direct |
| Objective. | current device employed in the treatment of mild to moderate inflammatory acne after 12 weeks of every other day use. |
| Design: | Male and female subjects will be enrolled in this single-site monadic study to evaluate the effect of a device on acne treatment. Subjects who sign the consent form and meet all inclusion criteria and none of the exclusion criteria will be enrolled at the baseline visit. Subjects will be asked to continue use of their self-selected moisturizer, non-medicated cleanser, and sunscreen they have used without difficulty for the prior 30 days and for the 12-week study. Subjects must also continue all facial products and cosmetics unchanged for the duration of the study. No other oral or topical acne products can be used. Subjects must be washed out of all topical acne products for at least 2 weeks and all oral acne products for at least 4 weeks prior to study participation. Subjects must possess mild to moderate acne with 5-30 inflammatory lesions and no nodules/cysts. |

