- 10. Subjects who have a history of a psychological illness or condition that would interfere with their ability to understand and follow the requirements of the study.
- 11. Subjects who have undergone recent facial surgery.
- 12. Subjects currently participating in any other clinical trial.
- 13. Subjects having started hormone replacement therapies (HRT) or hormones for birth control less than 3 months prior to the study entry; or who plan on starting, stopping or changing doses of HRT or hormones for birth control during the study.
- 14. Subjects who have a cardiac pacemaker, implanted defibrillator, or other implanted metallic or electronic device.
- 15. Subjects who are wearing EKG monitoring equipment.
- 16. Subjects with phlebitis, thrombophlebitis, broken capillaries, or varicose veins.
- 17. Subjects who have seizures, epilepsy, or cancer/tumors.
- 18. Subjects who have a history of hypertrophic scarring or keloid formation.

Endpoints:

Tolerability Endpoint:

The tolerability endpoint is the investigator-assessed absence of skin irritation from the facial study device at any time during the 12-week study.

Safety Endpoint:

The safety endpoint is the overall incidence of all adverse events reported during the study.

Efficacy Endpoint: The efficacy endpoint is the investigator assessed improvement in investigator global assessment (IGA) after 12 weeks of every other day device use as compared to baseline.

Measures:

Dermatologist Investigator assessed efficacy parameters: Investigator global acne assessment (IGA) based on the following 5 point ordinal scale: 0=clear, 1=almost

clear, 2=mild, 3=moderate, and 4=severe. IGA assessments will be conducted at baseline, week 2, week 4, week 8, and week 12.

Dermatologist Investigator lesion counts: inflammatory lesion count (papules, pustules), non-inflammatory lesion count (open comedones, closed comedones). Lesion counts will be conducted at baseline, week 2, week 4, week 8, and week 12.

Dermatologist Investigator assessed tolerability parameters: peeling, dryness, redness, and swelling. All assessments will be made on a 5-point ordinal scale (0=none, 1=minimal, 2=mild, 3=moderate, & 4=severe) at baseline, week 2, week 4, week 8, and week 12.

Self-assessment questionnaire: To be provided by sponsor. All assessments will be at week 2, week 4, and week 8, and week 12.

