Subject assessed tolerability parameters: itching, burning, redness, and swelling. All assessments will be made on a 5-point ordinal scale (0=none, 1=minimal, 2=mild, 3=moderate, & 4=severe) at baseline, week 2, week 4, and week 8, and week 12.

Photography: all investigator selected subjects will be photographed with the Canfield VISIA CR using Standard 1 lighting at baseline, week 2, week 4, and week 8, and week 12.

Statistical Methods:

Along with descriptive statistics (means, standard deviations and percentages), investigator and subject ordinal nonparametric data will be analyzed using the Wilcoxon signed rank test. Acne lesion counts will be assessed using a Student t test. Change will be considered significant at a p value of less than or equal to 0.05.

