9.1 COMPLETED, DISCONTINUED OR INCOMPLETE SUBJECTS

A completed subject is a subject who has satisfied all study entry criteria and completed the 12-week study. For any subject who has started study and terminated from the study prematurely, every effort will be made to obtain final evaluations of clinical status. Reasonable effort will be made to contact any subject lost to follow-up during the course of the study in order to complete assessments and retrieve any outstanding data and clinical supplies. The investigator will choose the description that best describes the status of the subject at termination.

1. Subject completed the 12 week study period

OR INCOMPLETE/DISCONTINUED DUE TO:

- 2. Contact dermatitis
- 3. Adverse experience
- 4. Serious adverse experience
- 5. Pregnancy
- 6. Protocol violation
- 7. Subject withdrew consent
- 8. Subject lost due to follow-up issues (e.g., attendance issues)
- 9. Other (provide reason)

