10.5 STORAGE AND ACCOUNTABILITY OF STUDY PRODUCT

The study product will be stored at room temperature, away from sunlight, in a locked, limited access area at the study site. Access to the study product will be limited to the investigator and staff members designated to dispense study medication. A study product log will be used to record the dispensation and return of all study products. The subject number/initials, and the initials and date of the person dispensing and receiving the returned study product will be documented on this form.

10.6

CODE DISCLOSURE

The study coordinator will not develop a code as all subjects will use the active device and electroconductive media in this monadic study.

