12. STATISTICAL METHODS

The statistical evaluation will be performed by Dermatology Consulting Services. Along with descriptive statistics (means, standard deviations and percentages), investigator and subject ordinal nonparametric data will be analyzed using the Wilcoxon signed rank test. Acne lesion counts will be assessed using a Student t test. Change will be considered significant at a p value of less than or equal to 0.05.

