12.1 SAMPLE SIZE RATIONALE

A sample size of 50 study subjects was chosen by the study sponsor.

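### The title page names a historical control that the supplied plan never defines or uses, and the planned tests of change from baseline cannot by themselves demonstrate device efficacy

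*Combined protocol and SAP*

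**What the plan says.** The Study Design row of the title page reads "Monadic device, historical control". The term does not recur in the supplied text. The synopsis and Sections 5 and 7.2.1 call the study single-site and monadic, and Section 10.6 (Code Disclosure) says that "all subjects will use the active device and electroconductive media in this monadic study".

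The synopsis begins its objective with "The objective of this study is to demonstrate the safety and efficacy of a novel direct" current device, and Section 4 says the same.

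The only named efficacy endpoint (synopsis and Section 12.5) is the "improvement in investigator global assessment (IGA) after 12 weeks of every other day device use as compared to baseline". Ordinal data are to be analysed by the Wilcoxon signed-rank test. For lesions, the synopsis and Section 12 say "Acne lesion counts will be assessed using a Student t test", without stating pairing or a reference value. The criterion in both places is "Change will be considered significant at a p value of less than or equal to 0.05"; Section 12.2 makes the test two-sided. The whole of Section 12.1 is "A sample size of 50 study subjects was chosen by the study sponsor".

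**The concern.** A historical control is an external comparison: a stated value or dataset, with a reason to think it comparable, against which the single arm is judged. The title page promises one and the operative sections do not supply it. If the label loosely meant each subject's own baseline, it is a misnomer, and the same limit on inference applies.

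The limit matters because of the objective. In one open arm, a rejected hypothesis of no change is compatible with a device effect. It is equally compatible with the natural course of acne, regression to the mean, an effect of the gel, or expectation in an investigator who knows that everyone is treated. Eligibility and baseline are set at the same visit, so regression to the mean is possible. The entry window of 5 to 30 inflammatory lesions is bounded at both ends, so its direction is unknown.

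The plan does control some things: facial products and prescription medicines stay unchanged, other acne products are barred, and changes in hormone therapy are excluded. None of this separates the device from the sources just listed. At stake is whether a significant result is reported as proof of efficacy or as a change from baseline.

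**Working it through.** **1. The plan's own figure.** N = 50 cannot be reproduced. Section 12.1 gives no effect size, SD, response rate, historical reference, power or dropout allowance. For orientation, the standardised within-subject change detectable with 80% power at two-sided 0.05 is (1.960 + 0.842)/√50 = 0.40 SD. That is power to detect any change from baseline, not a device effect.

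**2. What would have to be present for a historical control.**

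| Element | Where it would stand | What is there |
|---|---|---|
| Source and value | Synopsis, Sections 12 and 12.5 | Nothing |
| Endpoint defined against it | Synopsis endpoints, Section 12.5 | Comparison with baseline |
| Test against it | Synopsis methods, Sections 12 and 12.2 | Tests of change at 0.05 |
| Sample size built on it | Section 12.1 | Sponsor's choice |

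**3. What the 0.05 level controls.** It limits error when there is no change. It does not limit error when there is change but no device effect. To illustrate, suppose the device is inert and a proportion a of subjects improves, and b worsens, by one IGA grade. These rates are assumptions; the documents give none.

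With one-grade shifts all non-zero differences tie, so the signed-rank test reduces to the sign test. The number who change is M ~ Binomial(N, a + b). Given M, the number who improve is K ~ Binomial(M, a/(a + b)). The result is a significant improvement when K > M/2 and 2·P(Bin(M, ½) ≥ K) ≤ 0.05. For M = 10 this needs 9 improvers: 2 × (10 + 1)/1024 = 0.021. For M = 15 it needs 12: 2 × 576/32768 = 0.035. Summing over M and K gives the chance of a significant IGA improvement:

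| Improve/worsen | Exact, N = 50 | Exact, N = 40 | Normal approximation, no continuity correction, N = 50 |
|---|---|---|---|
| 10%/20% | 0.02% | 0.03% | 0.05% |
| 10%/10% | 1.1% | 0.9% | 2.1% |
| 20%/20% | 1.5% | 1.4% | 2.6% |
| 20%/10% | 17.8% | 13.3% | 24.4% |
| 30%/10% | 54.7% | 44.0% | 64.2% |

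The plan states neither the form of the test nor an evaluable number. Section 9.1 says only that "every effort will be made to obtain final evaluations of clinical status" for subjects who stop early. Hence the alternative columns; 40 is an assumed figure. If one fifth of shifts are two grades (exact test, N = 50, simulated), the 10/10, 20/10 and 30/10 rows become about 1%, 18% and 54%.

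**4. Lesion counts.** Read as a paired t test (an inference, since the plan does not say so), the chance of a significant fall is P(T > t at 0.975), with T noncentral t on N − 1 degrees of freedom and noncentrality d√N. Here d is the background fall in SDs of the change. For N = 50: d = −0.2 gives 0.04%, 0.2 gives 28% and 0.3 gives 55%. For N = 40 the last two are 23% and 46%.

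The chance is negligible under unfavourable drift, small under balanced drift and substantial under net favourable drift. The plan contains no comparison that could tell these apart.

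**The case against.** The strongest reply is that only one title-page line is out of step. Every operative section consistently describes a single arm compared with baseline, and Section 12 speaks only of significant change. That a single arm cannot prove causation is true of any such study and is not a contradiction within this plan. This is fair as far as it goes: the data and planned tests remain usable. It does not dispose of the point, because both statements of the objective use *demonstrate*, and the only tests offered in support are tests of change.

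The second reply is that the supplied text cannot show what the sponsor meant or holds. This stands. A reader might infer that no historical control exists. The documents do not support that: part of the document was not available, and Section 15 is listed in the contents but was not supplied. Nothing suggests that Section 15 holds a control, but the choice between the two readings belongs to the sponsor.

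The third is that the illustration rests on chosen drift rates. This also stands, which is why unfavourable and balanced cases are shown. A reader might take 55% or 64% as this trial's false-positive rate; the documents give no drift from which any such rate could be derived.

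Finally, the gel is part of the studied regimen (Sections 7.1.5 and 10.1), so its contribution may be intended. The objective, however, names only the device.

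**Conclusion.** The point holds for the supplied text and should be fixed. The title page states a design property that the endpoints, analyses and sample-size statement do not contain. A significant result under the plan would show change from baseline; it would not by itself demonstrate device efficacy. This follows from the design and does not depend on the drift figures. Those figures, from 0.02% to 55% in the main exact-test case, show only how far the answer turns on a quantity that the plan neither states nor can estimate.

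It would go too far to conclude that the device has no effect, that the signed-rank or t test is the wrong test of change, or that the study is without value. The documents support none of these.

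**What to change.** Before enrolment, the sponsor chooses one of two equal options.

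**(a) No external control.** Change the title-page design to: *Monadic device, open-label single arm, comparison with baseline, no external control.* In the synopsis objective and Section 4, replace the aim of demonstrating with: *assess the safety and estimate the 12-week change from baseline in IGA and lesion counts*, adjusting the rest of the sentence to fit. Add the same sentence to both statistical-methods paragraphs (synopsis and Section 12) so that they stay identical: *Test results describe change from baseline and do not by themselves establish device efficacy; the proportions improved, unchanged and worsened on IGA at week 12 (exact 95% CI, among subjects with a week-12 value, with the number missing stated) and the mean within-subject lesion-count change (95% t interval) will be reported.* Leave the endpoint definitions as they are.

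**(b) A real historical control.** Name the source, the reference value with its uncertainty, and the comparison, in the synopsis and Sections 12 and 12.5.

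Option (a) needs no extra subjects, visits or assessments. Its price is a more modest claim and limited precision: 20 of 50 improved would give 40% (exact 95% CI 26% to 55%). The revision needs written sponsor and IRB approval (Section 14.5), and the new text should be checked against the Investigational Device Exemption listed in Section 14.1.

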1. PROTOCOL SYNOPSIS

| Title of Study: | Evaluation of the Safety and Efficacy of an Acne Treatment Device |
|--|---|
| Study Period: | 12 weeks |
| Test Device and Application Instructions: | ZIIP Device (active) -400 microamps direct current, applied 3 days per week on non-consecutive days, on all areas afflicted by acne The following instructions will be provided: 1. Both silver probes must come in contact with skin throughout treatment. 2. Slowly make continuous circles with the top probe (the one farthest away from the charging port) over acne within each facial zone. **NOTE: Instructional video will be provided for participants to follow** 3. Treat each facial zone for 1 minute. Your device will beep and vibrate at the one minute mark to indicate that treatment of that zone is complete. Only treat the acne zone(s) identified for treatment. 4. After treatment, wipe your device clean with a tissue, being careful to avoid the charging port. Spray the device and a second tissue lightly with rubbing alcohol and wipe again, remaining careful to avoid the charging port. 5. Store safely away from water, moisture or debris. |
| Ancillary Product and Application Instructions: Objective: | Electroconductive Media Apply as a thin layer to all facial areas afflicted with acne The objective of this study is to demonstrate the safety and efficacy of a novel direct |
| Objective. | current device employed in the treatment of mild to moderate inflammatory acne after 12 weeks of every other day use. |
| Design: | Male and female subjects will be enrolled in this single-site monadic study to evaluate the effect of a device on acne treatment. Subjects who sign the consent form and meet all inclusion criteria and none of the exclusion criteria will be enrolled at the baseline visit. Subjects will be asked to continue use of their self-selected moisturizer, non-medicated cleanser, and sunscreen they have used without difficulty for the prior 30 days and for the 12-week study. Subjects must also continue all facial products and cosmetics unchanged for the duration of the study. No other oral or topical acne products can be used. Subjects must be washed out of all topical acne products for at least 2 weeks and all oral acne products for at least 4 weeks prior to study participation. Subjects must possess mild to moderate acne with 5-30 inflammatory lesions and no nodules/cysts. |
| | At baseline visit, subjects will receive the study acne device to be applied to the areas of the face afflicted by acne following cleansing, every other day. The dermatologist investigator will assess the face for the investigator global acne assessment (IGA) based on the following 5 point ordinal scale: 0=clear, 1=almost clear, 2=mild, 3=moderate, and 4=severe. In addition, the dermatologist investigator will perform |

an inflammatory and non-inflammatory lesion count. The dermatologist investigator will assess the tolerability of the device in terms of peeling, dryness, redness, and swelling on a 5-point ordinal scale (0=none, 1=minimal, 2=mild, 3=moderate, & 4=severe).

The subjects will assess device tolerability in terms of itching, burning, redness, and swelling. All assessments will be made on a 5-point ordinal scale (0=none, 1=minimal, 2=mild, 3=moderate, & 4=severe). Subjects will be given their diaries, study device, and electroconductive media and asked to return to the research center in 2 weeks. A reminder text will be sent to encourage compliance prior to the week 2 visit.

Subjects will return to the research center at week 2, week 4, and week 8 for the same study activities as conducted at baseline. However, in addition a subject self-assessment marketing questionnaire provided by the sponsor will be administered. Subject diaries will be checked at each return visit for compliance and completion. Subjects will be re-dispensed electroconductive media as needed at each visit; and the devices will be inspected for continued functionality. Reminder texts will be sent prior to each visit to encourage compliance.

Subjects will return to the research center at week 12 for the same study activities as conducted at baseline. Study diaries and devices will be checked and collected. Subjects will terminate their study participation at this time.

All investigator selected subjects will be photographed with the Canfield VISIA CR using Standard 1 lighting at baseline, week 2, week 4, and week 8, and week 12.

Subjects will be provided with the following device instructions:

- 1. Begin with clean, dry skin.
- 2. Inspect your skin and identify which zones of your face have acne. The four facial zones are divided as follows: 1) Upper Left, 2) Upper Right, 3) Lower Left, and 4) Lower Right. The zone(s) identified now will be treated throughout the study.
- 3. Liberally apply the conductive gel provided to you over each zone which has acne.
- 4. Turn on your device by pressing the button at the top. You will hear one beep.
- 5. Place the device on your skin. Lights will illuminate under the device when both silver probes come in contact with your skin. Both probes must keep contact with skin throughout treatment.
- 6. Slowly make continuous circles with the top probe (the one farthest away from the charging port) over acne within each facial zone. (You may feel a tingling sensation during treatment. That is normal.)
- 7. Treat each facial zone for 1 minute. Your device will beep and vibrate at the one minute mark to indicate that treatment of that zone is complete. Only treat the acne zone(s) identified for treatment.
- 8. At the end of treatment, your device will beep twice and turn off.

- 9. After treatment, wipe your device clean with a tissue, being careful to avoid the charging port. Spray the device and a second tissue lightly with rubbing alcohol and wipe again, remaining careful to avoid the charging port.
- 10. Store safely away from water, moisture or debris. After treatment, wipe your device clean with a tissue before putting it away.
- 11. Repeat treatment of the original acne zone(s) through the study. Perform treatments every other day for 12 weeks.
- 12. If any new areas of acne develop later in the study, you may also treat those additional zones until study completion. For example, if you have acne in the forehead and mouth zones at the start of the study, treat those two zones for every treatment. If additional acne develops on the left cheek later in the study, treat the left cheek zone in addition to the mouth and forehead zones for all remaining treatments

CHARGING:

When you see the orange light flashing while using your device, it's time to charge. To charge, plug in the charging cable provided. The orange light will remain illuminated while charging. You will know that your device is completely charged when the orange light is no longer on.

CONTRAINDICATIONS

ZIIP should not be used in the following areas

- Breast area
- Directly on top of the eyelid
- Midline of neck (bone of neck)
- Groin area
- Do not use this device on patients who have a cardiac pacemaker, implanted defibrillator, or other implanted metallic or electronic device because this may cause electric shock

WARNINGS

Do not submerge the device in water or any other liquid(s). If you store your ZIIP in an area such as a bathroom counter, ensure the product does not come in contact with water or other liquid(s).

ZIIP should not be used by:

- Children
- Pregnant Women
- People subject to seizures
- People with cancer/tumors
- People with a cardiac pacemaker
- People with implanted defibrillators/stimulators
- People with electronic implanted devices

If you have any medical concerns, such as a severe medical illness, epilepsy or seizures, or recent facial surgery, please consult your doctor before using ZIIP.

| DΔ | GF | Q S | αf | 28 |
|----|-------------|------|------------|----|
| | · · · · · · | · () | ()1 | ~0 |

| Dermatology Consulting Services, PLLC | Dermatol | logy C | Consulting | Services. | PLLC |
|---------------------------------------|----------|--------|------------|-----------|------|
|---------------------------------------|----------|--------|------------|-----------|------|

| | Electronic monitoring equipment (such as ECG monitors and ECG alarms) may not operate properly when a ZIIP device is in use. |
|-------------|---|
| | Stimulation should not be applied over, or in proximity to cancerous lesions, or applied over swollen, infected, or inflamed areas or skin eruptions, e.g., phlebitis, thrombophlebitis, broken capillaries, varicose veins, etc. Men should shave before use as hair can interfere with the conductivity of the electrodes. Facial area under a beard or mustache cannot be treated. |
| | Do not apply stimulation across your chest as the introduction of electrical current into the chest may cause rhythm disturbances to your heart, which could be lethal. |
| | The long-term effects of stimulation are not known. |
| | (There is an allowance for an unscheduled visit at any time, if necessary.) |
| Study | Healthy male and female subjects 18-50 years of age of all Fitzpatrick skin types |
| Population: | with mild to moderate acne consisting of 5-30 inflammatory lesions and no nodules/cysts. |
| Number of | 50 subjects |
| Patients: | |
| Inclusion | 1. Subjects with mild to moderate acne (5-30 inflammatory lesions and no |
| Criteria: | nodules/cysts). |
| | 2. Male and female subjects age 18-50 years. |
| | 3. Subjects with all Fitzpatrick skin types. |
| | 4. Subjects of all complexion types (normal, oily, dry, combination). |
| | 5. Subjects who have used the same moisturizer without difficulty for 30 days and will continue using same moisturizer during the 12-week study. |
| | 6. Subjects agree not to introduce any new colored cosmetics (lipsticks, eye shadows, facial foundations, blush, or powder). |
| | 7. Subjects who are using no other acne products for the duration of the study. |
| | 8. No known medical conditions that, in the investigator's opinion, may interfere with study participation. |
| | 9. Women of childbearing potential must be willing to use a form of birth |
| | control during the study. For the purpose of this study, the following are considered acceptable methods of birth control: oral contraceptives, Norplant®, Depo-Provera®, double barrier methods (e.g., condom and |
| | spermicide) and abstinence. |
| | 10. Subjects have signed an Informed Consent Form in compliance with 21CFR, Part 50: "Protection of Human Subjects." |
| | 11. Subjects are dependable and able to follow directions and willing to comply |
| | with the schedule of visits. 12. Subjects in generally good physical and mental health. |
| Exclusion | 1. Any dermatological disorder, which in the investigator's opinion, may interfere |
| Criteria: | with the accurate evaluation of the subject's skin characteristics, except for the |
| Ciliona. | study condition of acne. |
| | y |

- 2. Subjects who are not willing to use the assigned study device to their face as instructed.
- 3. Subjects who have used any topical prescription or OTC acne products for 2 weeks prior to study entry.
- 4. Subjects who have taken any oral prescription or OTC acne products for 4 weeks prior to study entry.
- 5. Subjects who have used a non-OTC cleanser without benzoyl peroxide, sulfur or salicylic acid for at least 2 weeks prior to study entry.
- 6. Subject who have not had any facial treatments in the past 6 months and are willing to withhold all facial treatments during the course of the study including facials, facial peels, photo facials, laser treatments, dermabrasion, botulinum toxin (Botox), injectable filler treatments, intense pulsed light (IPL), acid treatments, tightening treatments, and/or facial plastic surgery.
- 7. Subjects who are pregnant, breast feeding or planning a pregnancy.
- 8. Subjects with clinically significant and/or unstable medical disorders.
- 9. Subjects who are unwilling or unable to comply with the requirements of the protocol.
- 10. Subjects who have a history of a psychological illness or condition that would interfere with their ability to understand and follow the requirements of the study.
- 11. Subjects who have undergone recent facial surgery.
- 12. Subjects currently participating in any other clinical trial.
- 13. Subjects having started hormone replacement therapies (HRT) or hormones for birth control less than 3 months prior to the study entry; or who plan on starting, stopping or changing doses of HRT or hormones for birth control during the study.
- 14. Subjects who have a cardiac pacemaker, implanted defibrillator, or other implanted metallic or electronic device.
- 15. Subjects who are wearing EKG monitoring equipment.
- 16. Subjects with phlebitis, thrombophlebitis, broken capillaries, or varicose veins.
- 17. Subjects who have seizures, epilepsy, or cancer/tumors.
- 18. Subjects who have a history of hypertrophic scarring or keloid formation.

Endpoints:

Tolerability Endpoint:

The tolerability endpoint is the investigator-assessed absence of skin irritation from the facial study device at any time during the 12-week study.

Safety Endpoint:

The safety endpoint is the overall incidence of all adverse events reported during the study.

Efficacy Endpoint: The efficacy endpoint is the investigator assessed improvement in investigator global assessment (IGA) after 12 weeks of every other day device use as compared to baseline.

Measures:

Dermatologist Investigator assessed efficacy parameters: Investigator global acne assessment (IGA) based on the following 5 point ordinal scale: 0=clear, 1=almost

clear, 2=mild, 3=moderate, and 4=severe. IGA assessments will be conducted at baseline, week 2, week 4, week 8, and week 12.

Dermatologist Investigator lesion counts: inflammatory lesion count (papules, pustules), non-inflammatory lesion count (open comedones, closed comedones). Lesion counts will be conducted at baseline, week 2, week 4, week 8, and week 12.

Dermatologist Investigator assessed tolerability parameters: peeling, dryness, redness, and swelling. All assessments will be made on a 5-point ordinal scale (0=none, 1=minimal, 2=mild, 3=moderate, & 4=severe) at baseline, week 2, week 4, week 8, and week 12.

Self-assessment questionnaire: To be provided by sponsor. All assessments will be at week 2, week 4, and week 8, and week 12.

Subject assessed tolerability parameters: itching, burning, redness, and swelling. All assessments will be made on a 5-point ordinal scale (0=none, 1=minimal, 2=mild, 3=moderate, & 4=severe) at baseline, week 2, week 4, and week 8, and week 12.

Photography: all investigator selected subjects will be photographed with the Canfield VISIA CR using Standard 1 lighting at baseline, week 2, week 4, and week 8, and week 12.

Statistical Methods:

Along with descriptive statistics (means, standard deviations and percentages), investigator and subject ordinal nonparametric data will be analyzed using the Wilcoxon signed rank test. Acne lesion counts will be assessed using a Student t test. Change will be considered significant at a p value of less than or equal to 0.05.

